8.2 Second Malignancy

A second malignancy is one unrelated to the treatment of a prior malignancy (and is **NOT** a metastasis from the initial malignancy).

STUDY CLOSE-OUT

Any study report submitted to the FDA by the Sponsor-Investigator should be copied to Genentech. This includes all IND annual reports and the Clinical Study Report (final study report). Additionally, any literature articles that are a result of the study should be sent to Genentech. Copies of such reports should be mailed to the assigned Clinical Operations contact for the study:

[Clinical Operations Contact Information

l [contact]

And to Genentech Drug Safety CTV oversight mail box at: ctvist [contact]

QUERIES

Queries related to the Study will be answered by the [name] or study staff. However, responses to all safety queries from regulatory authorities or for publications will be discussed and coordinated between the Parties. The Parties agree that Genentech shall have the final say and control over safety queries relating to the Product. [name] agrees that it shall not answer such queries from regulatory authorities and other sources relating to the Product independently but shall redirect such queries to Genentech.

Both Parties will use all reasonable effort to ensure that deadlines for responses to urgent requests for information or review of data are met. The Parties will clearly indicate on the request the reason for urgency and the date by which a response is required.

SAFETY CRISIS MANAGEMENT

In case of a safety crisis, e.g., where safety issues have a potential impact on the indication(s), on the conduct of the Study, may lead to labeling changes or regulatory actions that limit or restrict the way in which the Product is used, or where there is media involvement, the Party where the crisis originates will contact the other Party as soon as possible.

The Parties agree that Genentech shall have the final say and control over safety crisis management issues relating to the Product. [name] agrees that it shall not answer such queries from media and other sources relating to the Product but shall redirect such queries to Genentech.

COMPLIANCE WITH PHARMACOVIGILANCE AGREEMENT / AUDIT

The Parties shall follow their own procedures for adherence to AE reporting timelines.

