13.1.2 Responsibility for Data Submission

Study staff are responsible for submitting data and/or data forms in ONCORE per Winship SOP 4.2 Data Completion Metrics. Data completion will be reviewed monthly. In situations where there are significant delays of data completion, the PI may temporarily suspend enrollment. Data entry is to be completed within the designated timeframe, not to exceed 30 days of the subject visit.

Queries will be resolved by the research staff within the time frame specified by the protocol, not to exceed 2 weeks.

The Data and Safety Monitoring Committee (DSMC) of the Winship Cancer Institute will provide oversight for the conduct of this study. The DSMC functions independently within Winship Cancer Institute to conduct internal monitoring functions to ensure that research being conducted by Winship Cancer Institute Investigators produces high-quality scientific data in a manner consistent with good clinical practice (GCP) and appropriate regulations that govern clinical research. Depending on the risk level of the protocol, the DSMC review may occur every 6 months or annually. For studies deemed High Risk, initial study monitoring will occur within 6 months from the date of the first subject accrued, with 2 of the first 5 subjects being reviewed. For studies deemed Moderate Risk, initial study monitoring will occur within 1 year from the date of the first subject accrued, with 2 of the first 5 subjects being reviewed. Subsequent monitoring will occur in routine intervals per the Winship Data and Safety Monitoring Plan (DSMP).

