The DSMC will review pertinent aspects of the study to assess subject safety, compliance with the protocol, data collection, and risk-benefit ratio. Specifically, the Winship Cancer Institute Internal Monitors assigned to the DSMC may verify informed consent, eligibility, data entry, accuracy and availability of source documents, AEs/SAEs, and essential regulatory documents. Following the monitoring review, monitors will provide a preliminary report of monitoring findings to the PI and other pertinent individuals involved in the conduct of the study. The PI is required to address and respond to all the deficiencies noted in the preliminary report. Prior to the completion of the final summary report, monitors will discuss the preliminary report responses with the PI and other team members (when appropriate). A final monitoring summary report will then be prepared by the monitor. Final DSMC review will include the final monitoring summary report with corresponding PI response, submitted CAPA (when applicable), PI Summary statement, and available aggregate toxicity and safety data.

The DSMC will render a recommendation and rating based on the overall trial conduct. The PI is responsible for ensuring that instances of egregious data insufficiencies are reported to the IRB. Continuing Review submissions will include the DSMC recommendation letter. Should any revisions be made to the protocol-specific monitoring plan after initial DSMC approval, the PI will be responsible for notifying the DSMC of such changes. The Committee reserves the right to conduct additional audits if necessary.

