14.2 Sample Size/Accrual Rate

This is an open-label, 2-arm phase II clinical trial to study the differential effect in the risk of IRAEs between treatment and control groups. A sample size of 22 patients per arm (44 total) will provide us approximately 80% power to detect a 40% difference in the rates of developing ≥grade 3 IRAE within 6 months follow up between the control and the treatment arm (estimated to be 60% in the control arm, Callahan et al; J Clin Oncol. 2017 Dec 1;35(34):3815-3822). The sample size calculation is based on Fisher's exact test at a one sided significance level of 0.05 under the following assumptions: 1). Patients will be randomized in 1:1 ratio of the treatment to control arm. 2). Approximately 60% patients in the placebo arm will develop > grade 3 IRAE

within 6 months based on our pilot study. 3). The treatment will reduce the rate of ≥ grade 3 IRAE to 20% in the treatment arm. In a recent study, the rate of objective response following combination checkpoint blockade was 42% (Callahan et al; J Clin Oncol. 2017 Dec 1;35(34):3815-3822). In order to monitor potentially adverse impact of Rituxan on checkpoint blockade, we will utilize early stopping rules based on an adaptive design wherein trial will be stopped if we have strong evidence of rates of objective response of <30%. The trial will be stopped early in the unlikely event that less than 2 patients among the first 12 patients treated by Rituxan respond to therapy. If the rate of objective response is > 30%, the probability that at least two out of first twelve patients will achieve an objective response of at least a PR for the first 12 patients is approximately 92%. Hazard ratios and corresponding two-sided 95% confidence intervals will be estimated using Cox-proportional hazards model, with the treatment group as a single covariate. Progression-free and overall survival curves, median with 95% confidence intervals, and progression-free survival rates at 6 months will be estimated with the use of Kaplan-Meier method. Biostatistics support for the study will be provided by biostatistics core resource of Winship Cancer Center.

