Newly diagnosed patients as well as patients that have previously received anti-PD-1 therapy in adjuvant setting will be randomized as separate groups equally between the two arms. This will allow us to normalize the ORR between the two groups. ORR will be calculated for every 10 patients enrolled. The trial will be stopped early if there is a difference in ORR of greater than 30% between the two arms.

REFERENCES

- 4. Wolchok JD. PD-1 Blockers. Cell. 2015;162(5):937.

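### Both trial-level stopping rules count tumour response; in the supplied text no count of severe IRAEs or deaths calls the DSMC between its 6- or 12-monthly reviews (a cheap improvement, not an error)

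*Combined protocol and SAP*

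**What the plan says.** Section 14.1 makes the rate of grade 3 or greater IRAEs at 6 months the primary endpoint. Section 14.2 assumes 60% in controls and 20% with Rituxan, 22 patients per arm, tested one-sided at 0.05.

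The same section gives two early stops. Under the first, the "trial will be stopped if we have strong evidence of rates of objective response of <30" per cent; its working form is fewer than 2 responders among the first 12 Rituxan patients. The second: "The trial will be stopped early if there is a difference in ORR of greater than 30% between the two arms", with ORR calculated for every 10 patients enrolled.

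Safety oversight appears elsewhere:

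- Section 13.1.2: "Depending on the risk level of the protocol, the DSMC review may occur every 6 months or annually". This trial's risk level is not given. At moderate risk, "initial study monitoring will occur within 1 year from the date of the first subject accrued". The DSMC assesses subject safety and risk-benefit, its final review includes "available aggregate toxicity and safety data", and "The Committee reserves the right to conduct additional audits if necessary".
- Section 7.3: serious grade 3-5 events go within 24 hours to the IRB, FDA and the drug supplier. The DSMC is not named on that route.
- Section 6: Rituxan-related toxicity of grade 3 or more ends Rituxan for that patient only.
- Safety crisis clause (under section 8.2): "the Party where the crisis originates will contact the other Party as soon as possible". The parties are the sponsor and the supplier, and no count is given.

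Section 13.1.2 also relies on an institutional monitoring plan and mentions a protocol-specific one ("Should any revisions be made to the protocol-specific monitoring plan after initial DSMC approval"). Neither was supplied.

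**The concern.** Rituxan is added in the hope of lowering severe IRAEs, but it could raise severe toxicity. The primary test looks only for a reduction, and only at the end. Neither stopping rule takes a toxicity or death count as input, so an excess in Arm B would affect them only through its effect on response. The one written suspension of enrolment, in section 13.1.2, is for late data entry.

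Calendar review can be late in a trial this small. Aggregate tables, if pooled over arms, could also mask an Arm B excess when 60% is expected in controls. Investigators see toxicity by arm because the trial is open-label, but nothing says what number should prompt them to call the DSMC. At stake are the Arm B patients who would be enrolled between the time an excess becomes visible and the next scheduled review.

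**Working it through.** **1. The plan's own figure.** With ORR 30%, P(at least 2 of 12 respond) = 1 − 0.7^12 − 12 × 0.3 × 0.7^11 = 1 − 0.014 − 0.071 = 0.915. Section 14.2 says about 92%, so the figure is right. It describes response only.

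**2. Timing.** Accrual is not stated. At r Arm B patients per month, evenly spaced, the 22nd is enrolled at month 21/r: month 21 at r = 1, 10.5 at r = 2 and 5.25 at r = 4. If the first review falls at exactly month 12 (r = 2) or month 6 (r = 4), Arm B is already full.

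**3. An illustrative count.** Boundary: 6/6, 10/12 or 14/18 Arm B patients with a grade 3 or greater IRAE within 6 months. It comes from an assumed Beta(0.6, 0.4) prior and the criterion Pr(rate > 60%) > 0.90. The chance of reaching it is the sum of the first-crossing probabilities at n = 6, 12 and 18 (exact binomial). At a true rate of 60% the first term is 0.6^6 = 0.047.

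| True Arm B rate | at 6 | at 12 | at 18 | total |
|---|---|---|---|---|
| 20% | <0.001 | <0.001 | <0.001 | 0.0001 |
| 60% | 0.047 | 0.058 | 0.040 | 0.144 |
| 65% | 0.075 | 0.102 | 0.074 | 0.252 |
| 70% | 0.118 | 0.165 | 0.118 | 0.401 |
| 80% | 0.262 | 0.322 | 0.175 | 0.759 |

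At 90% the total is 0.977. Moving the criterion between 0.80 and 0.95 moves the total from 36% to 11% at a true 60%, and from 91% to 64% at 80%.

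**4. Exposures avoided.** This was simulated, with 40,000 trials per setting. Assumptions: even accrual; equal arms; IRAE onset uniform over 0-6 months; ORR 42% in both arms, known 12 weeks after enrolment; both ORR rules active. The second ORR rule is read either in both directions or only with Arm B worse, which contributes to the ranges. The comparator is a DSMC that acts on the same counts at exactly every 6 or 12 months. The call is taken to lead to a prompt pause.

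Mean Arm B enrolment at a true 80%:

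| Arm B per month | 6-monthly DSMC | 12-monthly DSMC | with the call |
|---|---|---|---|
| 1 | 14.4-16.4 | 15.0-17.2 | 12.8-14.4 |
| 2 | 17.4-19.4 | 17.7-19.9 | 15.8-17.3 |
| 4 | 20.0-21.0 | 20.0-21.0 | 19.8-20.8 |

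Differences are taken within the same reading of the ORR rule and before rounding. At 1 per month, for example, 14.4 − 12.8 = 1.6 at the low end and 17.2 − 14.4 = 2.8 at the high end. At 2 per month the saving is 1.6-2.5, and at 4 per month it is under 0.2. At a true 70% the savings are 0.8-1.4, 0.7-1.1 and under 0.1.

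**5. Sensitivity.** At 0.5 Arm B patients per month the saving is 1.0-2.2 at 80% and 0.5-1.1 at 70%. At 0.25 per month it is 0.5-1.0 and 0.2-0.6. If onset is over 0-3 months instead, the saving at 4 per month and 80% is about 2 (2.3-2.7 in this model) and not under 0.2.

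**The case against.** The strongest reply is that this is a preference. The plan has DSMC review of safety and risk-benefit, discretionary audits, 24-hour reporting of serious events, expedited reporting of deaths and patient-level Rituxan discontinuation. Relying on judgement instead of a count is a legitimate design choice, and the natural home for a trigger is a monitoring plan that we have not seen. All of that stands, and it is why the point is an improvement only.

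Three further objections also stand in part:

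- **The count is set against a fixed 60%, not the randomised controls.** If the true control rate is 65-70% and Rituxan is inert, the count is still reached in 25-40% of trials. An automatic accrual pause would therefore be wrong. The count should only call a review, and the DSMC should read it against concurrent Arm A.
- **The savings lean on assumptions.** Section 13.1.2 sets an outer limit for the first monitoring, so an earlier review complies and shrinks the gain. The IRB, FDA, supplier and investigators are given no chance to act in the model.
- **A running count of the primary endpoint in an open-label trial could influence later grading.** Someone must also classify IRAEs, for which the protocol gives little beyond CTCAE grade. The first is a real cost. The second is needed for the primary analysis anyway.

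The count does not cover Rituxan-specific hazards such as infection. The documents give no acceptable rate from which to set a boundary for those.

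A reader might infer that the trial has no safety monitoring, or that no trigger exists. The documents support neither: oversight is written, and two monitoring plans are outside the supplied text.

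**Conclusion.** The gap holds for the supplied text: both trial-level rules count response, and no severe-IRAE or death count brings the DSMC in between scheduled reviews. It is not an error in the plan.

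The benefit is modest: about 1-3 Arm B exposures avoided at true rates of 70-80% with 1-2 Arm B patients per month, if accrual is paused promptly after the review and the alternative is a DSMC acting at exactly 6 or 12 months. It is smaller with very slow accrual or earlier reviews. At 4 per month and a true 80% it runs from under 0.2 to about 2, depending on IRAE onset. Accrual, onset and DSMC behaviour are all assumed, and the value of the death notice is not quantified. If Rituxan works as designed (20%), the call is almost never made.

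**What to change.** 1. In 13.1.2, state that DSMC toxicity and death tables are shown by arm.
2. Send any death not due to progression to the DSMC at once, alongside the existing IRB, FDA and supplier report.
3. In 14.2, add a prompt, non-binding ad hoc DSMC review when Arm B patients with a grade 3 or greater IRAE within 6 months reach 6 of the first 6, 10 of the first 12 or 14 of the first 18. The DSMC compares that count with the concurrent Arm A rate before recommending any accrual pause.

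If either monitoring plan already holds such a trigger, cite it in 14.2 instead.

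The cost is protocol wording, a running count and a by-arm table, built from data that section 13.1.1 already sends to ONCORE monthly. There are no added patients or procedures. The downsides are an occasional unneeded review (14% if Rituxan is inert at 60%, 25-40% at 65-70%) and the running count of an open-label primary endpoint. That count should stay with the statistician and the DSMC.

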11. STUDY CALENDAR

Schedules shown in the Study Calendar below are provided as an example and should be modified as appropriate.

Baseline evaluations are to be conducted within 3 weeks prior to start of protocol therapy. Scans and x-rays must be done \leq 4 weeks prior to the start of therapy. In the event that the patient's condition is deteriorating, laboratory evaluations should be repeated within 48 hours prior to initiation of the next cycle of therapy.

All protocol visits have a plus or minus 3 business day window.

Rituxan should be given after ipi/nivo infusion for subjects on Arm B. The timing of Rituxan is 1-2 days (preferably 1 day) following ipi-nivo infusion.

		1	ı	ı						1	1					
	Pre- Study	Wk 1	Wk 2	Wk 3	Wk 4	Wk 5	Wk	Wk	Wk 8	Wk 9	Wk 10	WK 12	Wk 13	WK 17	WK 21	Off Study
IPI 3mg/kg + Nivo 1mg/kg		X			X			X			X					
Nivo 480mg IV ^a													X	X	X	
Rituxan IV (loading dose)			X													
Rituxan SQ				X	X	X										
Informed consent	X															
Demographics	X															
Medical history	X															
Con Medications	X	X	X	X	X			X			X		X	X	X	X
Physical exam	X	X			X			X			X		X	X	X	X
Vital signs	X	X	X	X	X			X			X		X	X	X	X
Height	X															
Weight	X	X	X	X	X			X			X		X	X	X	X
Performance status	X	X			X			X			X		X			X
CBC w/diff, plts	X	X	X	X	X			X			X		X	X	X	X
Serum chemistry with LDH	X	X	X	X	X			X			X		X	X	X	X
EKG (12-lead)	X															
Adverse Event	X	X	X	X	X			X			X		X	X	X	X
Radiologic Evaluation ^b	X											X				
B-HCG	X															
Hepatitis B (HepB surface antigen and HepB core antibody), Hep C and HIV serology	X															
TSH, Free T, ACTH, cortisol	X				X			X			X		X	X	X	X
Blood correlative	X		X		X						X		X			X
Fresh Tissue Biopsy ^c	X				X											

^a given every 4 weeks starting at Week 13 for up to 13 doses.

^b CT scans n/c/a/p with contrast every 12 weeks for the first two years, then every 6 months for five years. MRI brain with contrast should be done at baseline, then every 6 months for patients with no history of CNS mets as per standard of care; every 3 months for those with a history of CNS metastases for two years, then every 6 months. CT head can be used for patients with a contraindication to MRI.

^C Tissue biopsy before week 4 is optional but encouraged whenever possible.

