APPENDIX A PERFORMANCE STATUS CRITERIA

ECOG Performance Status Scale		Karnofsky Performance Scale	
Grade	Descriptions	Percent	Description
0	Normal activity. Fully active, able to carry on all pre-disease performance without restriction.	100	Normal, no complaints, no evidence of disease.
U		90	Able to carry on normal activity; minor signs or symptoms of disease.
1	Symptoms, but ambulatory. Restricted in physically strenuous activity, but ambulatory and able	80	Normal activity with effort; some signs or symptoms of disease.
1	to carry out work of a light or sedentary nature (e.g. , light housework, office work).	70	Cares for self, unable to carry on normal activity or to do active work.
2	In bed <50% of the time. Ambulatory and capable of all self-care, but unable to carry out	60	Requires occasional assistance, but is able to care for most of his/her needs.
	any work activities. Up and about more than 50% of waking hours.	50	Requires considerable assistance and frequent medical care.
3	In bed >50% of the time. Capable of only limited self-care, confined to bed or chair more than 50% of waking hours.	40	Disabled, requires special care and assistance.
		30	Severely disabled, hospitalization indicated. Death not imminent.
4	100% bedridden. Completely disabled. Cannot carry on any	20	Very sick, hospitalization indicated. Death not imminent.
	self-care. Totally confined to bed or chair.	10	Moribund, fatal processes progressing rapidly.
5	Dead.	0	Dead.

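### The PFS and OS hazard ratios are planned from a treatment-only Cox model; a pre-specified companion model with baseline LDH would cost one sentence and guard against chance imbalance and loss of sensitivity in 44 patients

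*Combined protocol and SAP*

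**What the plan says.** Section 14.2 states: "Hazard ratios and corresponding two-sided 95% confidence intervals will be estimated". The same sentence fixes the model: the ratios are "estimated using Cox-proportional hazards model, with the treatment group as a single covariate". There is no adjusted model, stratified model or sensitivity analysis for PFS or OS, and no target hazard ratio, event count, power or test for either.

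The Study Calendar (section 11) marks "Serum chemistry with LDH" at Pre-Study, so a baseline LDH is scheduled for every patient. Section 3.1 sets the entry ceiling at 10 times the institutional upper limit of normal, so the ratio LDH/ULN is already needed to confirm eligibility. The calendar also marks "Performance status" at Pre-Study. Appendix A supplies the "ECOG Performance Status Scale", but section 3.1 sets no limit on it.

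Section 5.1 randomises 1:1 in blocks of 6. The only factor balanced there and in 14.2 is prior anti-PD-1 treatment. The two sections describe that factor differently (failure on single-agent therapy in one, adjuvant exposure in the other), which needs reconciling. Neither mentions LDH.

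**The concern.** Comparing 1-year PFS and OS is a secondary objective (section 1.2). Section 2.4 makes preserved tumour control a condition for the approach to be clinically viable. The hazard ratio is the only between-arm survival estimate for which the plan names a model.

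In 44 patients two things can blur it. A baseline factor that drives outcome can fall unevenly between arms by chance and shift the estimate. Leaving such a factor out of a Cox model also moves the hazard ratio towards 1 when there is a real effect, so harm and benefit both become harder to see. The value needed to address this is already collected, but the plan makes no provision to use it. Section 14.2 already accepts the general idea, since it balances prior treatment so that response rates can be compared fairly.

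**Working it through.** **The plan's own figures.** None is stated for PFS or OS. The primary calculation ("A sample size of 22 patients per arm (44 total) will provide us approximately 80% power", "Fisher's exact test at a one sided significance level of 0.05", with 60% against 20%) gives 79.1% by exact enumeration, so it reproduces. It does not involve the Cox model.

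**Chance imbalance.** Assume a binary factor present in 40% of patients, with X_A and X_B each Binomial(22, 0.4). Twenty points is 0.20 × 22 = 4.4 patients, so a difference of at least 5 is needed. Summing the joint probabilities, P(|X_A − X_B| ≥ 5) = 16.5%. The same sum at 25% and 50% prevalence gives about 12% and 17%.

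**Effect of an imbalance.** Simulation assumptions, none of them in the documents: exponential PFS with a 9-month median in the reference group, 12 to 36 months of follow-up, about 31 to 41 events, and one binary factor in 40%. A 20-point excess in Arm B multiplies the treatment-only hazard ratio by 1.09, 1.19 or 1.24 for a factor hazard ratio of 1.5, 2.5 or 4. The adjusted ratio moves by 2% or less.

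**Pull towards 1.** In the same setting a true hazard ratio of 2.0 averages 1.87 (factor 2.5) or 1.77 (factor 4) in the treatment-only model. With a true ratio of 1 there is no pull.

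**Precision.** The 95% interval runs from HR/k to HR × k with k = exp(1.96 × 2/√d) for d events. At d = 30, k = exp(0.716) = 2.05; at d = 40, k = exp(0.620) = 1.86.

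**Gain from log LDH alone.** Same 22 per arm and follow-up, with LDH as a standard-normal covariate on the log scale and a second factor (performance status) in 40% that also affects outcome but is left out of the model. Because the plan names no test, power here means the chance that the two-sided 95% interval excludes 1.

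| Assumed factors | True HR 2.0: treatment only, then with log LDH | True HR 0.5: treatment only, then with log LDH |
|---|---|---|
| Moderate | 43%, 51% (+8) | 37%, 44% (+7) |
| Strong | 37%, 49% (+12) | 33%, 44% (+11) |

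Weak factors give about 2 to 3 points; non-prognostic factors give essentially no change. A repeat run of 3,000 trials agreed with the table within about a point. It took weak, moderate and strong as LDH hazard ratios of 1.25, 1.6 and 2.0 per SD, with performance-status hazard ratios of 1.5, 2 and 2. The simulation standard error of one rate is at most √(0.5 × 0.5/3,000) = 0.9 points, hence a gain of about 7 to 13 points for moderate to strong factors.

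**Cost of one and of two covariates.** With log LDH alone, the RMSE of the log hazard ratio (against the conditional value) rises by at most about 0.02, and rejection under no effect is about 5 to 6%. With performance status added, at about 31 to 40 events:
- RMSE goes from 0.356 to 0.391 at a true ratio of 2.0 when neither factor matters.
- The estimate overshoots: 2.08 to 2.12 for a true 2.0, and 0.48 to 0.49 for a true 0.5.
- Rejection under no effect is 5.3 to 6.6%.

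**The case against.** The strongest case against has five parts.

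- **Nothing in the documents says that LDH predicts PFS or OS here.** This stands. The gain is a range conditional on an assumed strength, and at zero strength it vanishes.
- **The treatment-only ratio is not wrong.** This stands. A reader might infer that the planned estimate is biased or invalid. It estimates the marginal effect and rejects at about the nominal rate under no effect. The adjusted ratio is a different, conditional quantity.
- **A wide baseline spread is not shown.** This stands in part. A reader might infer from the ceiling of 10 times normal, and from the absence of a performance-status limit, that both factors vary widely. A ceiling is not a distribution, and patients must be clinically eligible for the combination and are treated as outpatients. The documents show only that LDH may range that far.
- **Adjustment has a price in a small trial.** This stands against two covariates and against replacing the planned model. It has little force against one covariate reported alongside.
- **The survival hazard ratios are secondary.** The listed endpoints are 1-year rates, and tumour control is monitored through response-rate stopping rules. Even a 20-point imbalance shifts the ratio by less than the interval's half-width factor of about 1.9 to 2.0. This limits the importance but does not remove the reason to pre-specify.

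OS deserves a separate caution. Section 5.3 follows patients for 4 weeks after removal from study, and progression leads to removal (sections 5.2 and 5.4). OS events may therefore be few, which adjustment does not cure. No OS simulation was run.

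**Conclusion.** The point holds as a modest, inexpensive improvement to a secondary analysis. The plan contains no adjusted survival estimate, although a baseline LDH is scheduled for every patient and is not balanced by design. A 20-point imbalance in a factor of 40% prevalence has about a 16% chance. Adjusting for LDH recovers 2 to 3 points of power if the factors are weak, 7 to 13 if they are moderate to strong, and essentially none if they are not prognostic.

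These figures assume a true hazard ratio of 2.0 or 0.5, exponential PFS with a 9-month median, about 31 to 41 events, and prognostic strengths that the documents do not supply. Neither model gives high power to detect a doubling of hazard in 44 patients.

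The documents do not support going further and treating the planned hazard ratio as invalid, replacing it, or adjusting for performance status as well. The primary comparison of grade 3 or greater immune-related events is untouched.

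**What to change.** Keep the treatment-only Cox model in section 14.2 and add one sentence. For PFS and for OS, a second Cox model will include treatment and one baseline covariate, log(LDH/ULN) from the Pre-Study sample, and its hazard ratio and two-sided 95% interval will be reported beside the treatment-only result. State that performance status is not part of this model.

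Fix the covariate and its form before any comparison of outcomes by arm. The trial is open-label and section 14.2 has response rates calculated every 10 patients, so the amendment should record which of those looks had already taken place. If OS events turn out to be few, say so beside the OS result.

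The cost is one sentence and one extra model per endpoint, with no new data, visits or patients. The statistical price is one more parameter, an RMSE of the log hazard ratio higher by up to about 0.02, rejection under no effect of about 5 to 6%, and a hazard ratio read as conditional on baseline LDH.
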